1.5 RISKS FOR CURRENT TREATMENT

Currently, treatment of women with cervical HSIL usually consists of either surgical removal of the affected tissue by CKC, LEEP, ablative therapy via laser, or cryotherapy. All treatments for cervical HSIL are associated with a variety of short and long term general and reproductive health risks as listed in Table 3.

CONFIDENTIAL

Page 26 of 87

Downloaded by

Surgical Treatments for Cervical HSIL	Risks
	Pain
	Exposure to anesthesia
	Heavy bleeding
	Infection
СКС	Menstruation problems
LEEP	Cervical stenosis (can lead to alteration of squamo-columnar junction)
Ablative therapy (Laser or	Shortening of the cervix
Cryotherapy)	Decreased fertility/difficulty getting pregnant
	Cervical incompetence
	Pre-term birth and elated low birth weight
	Incomplete treatment of cervical dysplasia
	Inadequate treatment of an occult early invasive cancer

Table 3: Risks Associated with Surgical Treatments for Cervical HSIL

Adapted from FAQs Loop Electrosurgical Excision Procedure (LEEP) American College of Obstetricians and Gynecologists (2014) [12].

More importantly, none of the currently available su gical tre tments for cervical HSIL eradicate the underlying cause of the high-grade cervical **dysplasia**, **persistent** infection with one or more of the high-risk HPV types, and therefore, leaves patients at risk for recurren' cervical HSIL as well as high grade dysplasia of the vulva and vagina due to the potentially broader infection of the genitourinary area.

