3.1.4 DEFINITION OF RESPONDER AND NON-RESPONDER

Responder and non-responder definitions (Table 4) for the primary endpoint takes into account both histopathologic regression of cervical HSIL and virologic (HPV-16 and/or HPV-18) clearance from cervical samples since HPV persistence is an important factor in the clinical progression of HSIL. The responder definition also excludes subjects who undergo excision or whose cervix is biopsied at any time after their initial dose and before the Week 36 endpoint tissue collection time frame. This exclusion is included to reduce the potential for artefactual increases in t a treatme. t effect caused by removal of HSIL tissue and potentially HPV-16/18 by unplanned interval biopsies.

To qualify as a responder for the primary endpoint, t z subject m. hav :

1) An acceptable histology specimen at the Week .6 time frame, which is interpretable by the independent PAC

2) An acceptable HPV ThinPrepTM sample at the Week .6 time frame, with an associated valid HPV-testing result.

A responder is defined as a subject wi ...:

- No histologic evidence of cervical HSIL
- No evidence of HPV-16 or HPV-18

- The subject must not have had an unscheduled excision or biopsy sample obtained between initial dose and the Week 36 evaluation.

To be qualified as a non-responder any subject with:

- Histologic evidence of cervica HSIL, or
- Evidence of HPV-16 or HPV-18, or
- An excision or biopsy sample obtained between initial dose and the Week 36 evaluation, or
- No Week 36 visit sample/result

Version Date: 01Jun2022

CONFIDENTIAL

Version 4.1

Page 29 of 87

Table 4: Definition of Composite Regression and Clearance Endpoint Responder and Non Responder

Responder	Non-Responder
	Subject with histologic evidence of cervical HSIL, AIS,
Subject with no histologic evidence of cervical	cervical carcinoma at Week 36 visit
HSIL ^a at Week 36 evaluation and no evidence of	OR
HPV-16 and/or HPV-18 at Week 36 visit ^b	Subject with evidence of HPV-16 or HPV-18 at Week 36 visit
AND	OR
Subject in whom an excision or biopsy sample ^c was	Subject in whom an excision or biopsy sample was obtained
NOT obtained between initial dose up to Week 36	between initial dose up to Week 36 visit
visit	OR
	Subjects with no Week 36 visit sample result

^a No evidence of HSIL is defined by histology as negative, squamous atypia, or LSIL

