6.12 CONCOMITANT MEDICATIONS/TREATMENTS

All medications (prescription and nonprescription) taken within 8 weeks prior to the screening biopsy date of eligible subjects must be recorded on the CRF. Actual or estimated start and stop dates must be provided. Medical procedures performed within 8 weeks prior to Screening biopsy date of eligible subjects that do not affect subject's eligibility for participation and during the study (including over the counter or herbal), will be recorded on the CRFs. This information will be obtained from the subject and abstracted from any available medical records. The indication for the medication, dose, and dose regimen will be documented. Medication that is considered necessary for the subject's safety and well-being may be given at the discretion of the investigator and recorded in the appropriate sections of the CRF.

Version Date: 01Jun2022

CONFIDENTIAL

Version 4.1

Page 62 of 87

The following medications and treatments are prohibited:

- Long term use (\geq 7 days) of oral or parenteral glucocorticoids at a dose of \geq 20 mg/day of prednisone equivalent; use of inhaled otic and ophthalmic corticosteroids are allowed
- Disease modifying doses of anti-rheumatic drugs (e.g., azathioprine, cyclophosphamide, cyclosporine, methotrexate), and biologic disease modifying drugs such as TNF-α inhibitors (e.g. infliximab, adalimumab or etanercept) at screening and throughout the study
- Administration of any non-study related, non-live vaccine within 2 weeks of any study treatment or within 4 weeks of any study treatment for any non-study, live vaccine
- Blood thinners (e.g. anticoagulants, antiplatelet drugs) or other medication that affects blood clotting within 2 to 14 days (e.g., 4-5 drug half-lives) of any study treatment, biopsy or excisional procedure (e.g. LEEP)

The decision to administer a prohibited medication/treatment is done with the safety of the study participant as the primary consideration. When possible, the Sponsor should be notified before the prohibited medication/treatment is administered. All medications should recorded in the appropriate sections of the subject's eCRF.

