8.5.9 MISSING VALUES

Missing data will be considered as non-regressors (failures) for the ITT efficacy analyses. A subject's regression outcome is missing if the CIN grade and HPV clearance at the Week 36 time frame cannot be determined. Also, any subject who undergoes an unscheduled excision or biopsy in which cervical tissue sample is obtained after Dose 1 and before the Week 36 timeframe will be considered a non-regressor regardless of the Week 36 timeframe result.

Efficacy analyses using the mITT population will be co jucted and will serve as sensitivity analyses regarding missing data.

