4.3. Analysis Population

4.3.1. Intent-to-Treat

The intent to treat (ITT) population includes all subjects who are randomized. Subjects in this sample will be grouped to treatment arms as randomized. Analysis of the ITT biomarkerpositive population will be primary for the analysis of efficacy in this study. Missing data will be considered as non-regressors (failures) for the ITT efficacy analysis. A subject's regression outcome is missing if her CIN grade and HPV clearance at the Week 36 timeframe cannot be determined. Also, any subject who undergoes excision or whose cervix is biopsied at any time between their initial dose and the Week 36 timeframe will be considered a non-regressor regardless of the Week 36 timeframe result. The ITT population will also be used for summaries of demographics, baseline characteristics, and disposition and protocol deviations.

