8.1.1. Primary Efficacy Endpoint

The primary efficacy endpoint is the proportion of baseline biomarker-positive subjects with no evidence of cervical HSIL (i.e., no evidence of CIN2, CIN3) on histology sample and no evidence of HPV-16 and/or HPV-18 in cervical samples by type specific HPV testing at the Week 36 timeframe.

The primary hypothesis of superiority is:

H₀: $\delta \leq 0$ vs. H₁: $\delta > 0$,

where $\delta = Pv - Pp$, and Pv and Pp denote the true biomarker-positive population probabilities of the primary endpoint for VGX-3100 and Placebo, respectively. The proportion in each treatment arm is calculated by the number of responders divided by the total number of responders and non-responders in the study population of the corresponding treatment arm. The detailed definitions of responder and non-responder are listed in Table 1.

For the primary endpoint, week 36 histology is evaluated based on the first biopsy or surgical excision procedure on or after Day 238; in case of multiple results on the same day, the one with worst grade will be used. The virology results used for analysis must be the latest result that is on or before the same date as the histology result and is taken on or after Day 238. If

a subject undergoes excision or cervical biopsy at any time on or after Day 1 and before Day 238, the subject will be considered as non-responder. Number of responders and non-responders, proportion of responders in each treatment arm, and difference of proportions between the two treatment arms will be presented. A p-value of superiority based on a test of risk difference and corresponding 95% confidence interval using the method of Miettinen and Nurminen [5] will be computed. Superiority will be concluded if the one-sided p-value is <0.025 and the corresponding lower bound of the 95% CI exceeds zero.

Responder proportion will also be summarized based on the stratification factors separately.

Responder	Non-Responder

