Subject with no histologic evidence of cervical HSIL ^a at Week 36 evaluation and no evidence of HPV-16 and/or HPV-18 at Week 36 ^b AND Subject in which an excision or biopsy sample ^c was NOT obtained between initial dose up to Week 36	Subject with histologic evidence of cervical HSIL, Adenocarcinoma-in-situ (AIS), cervical carcinoma at Week 36 OR Subject with evidence of HPV-16 or HPV-18 at Week 36 OR Subject in which an excision or biopsy sample was obtained between initial dose up to Week 36 OR Subjects with no Week 36 sample result

Table 1. Definition of Primary Endpoint Responder and Non-Responder

a. No evidence of HSIL is defined by histology as negative, squamous atypia, or LSIL

b. The histopathologic efficacy time frame is defined by those who have undergone a biopsy or surgical excision at any time starting from 14 days prior to the protocol-specified target date of Week 36. The first tissue removal sample in this time frame determines the histology endpoint. The most recent HPV clearance result prior to tissue removal, which includes results from the same date, within the time frame determines the HPV clearance endpoint.

c. Excludes ECC-only samples

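### The interval non-responder rule covers only excision and biopsy, so a woman whose lesion is ablated or otherwise treated before Week 36 can count as a responder in the ITT and mITT analyses

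*SAP*

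**What the plan says.** The interval-procedure rule appears in several places, always limited to the same two procedures:

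- SAP 8.1.1: a woman who "undergoes excision or cervical biopsy at any time on or after Day 1 and before Day 238, the subject will be considered as non-responder".
- SAP Table 1, non-responder column: "Subject in which an excision or biopsy sample was obtained between initial dose up to Week 36". SAP Table 2 repeats this for the secondary cervical endpoints.
- SAP 4.3.1 (ITT): "any subject who undergoes excision or whose cervix is biopsied at any time between their initial dose and the Week 36 timeframe" is a non-regressor whatever the Week 36 result.
- Protocol 3.1.4: "An excision or biopsy sample obtained between initial dose and the Week 36 evaluation". Protocol Tables 4 to 9 and section 8.5.1 follow it.
- Protocol 8.5.9: "any subject who undergoes an unscheduled excision or biopsy in which cervical tissue sample is obtained after Dose 1" and before the Week 36 time frame.

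Protocol 3.1.4 explains that the rule guards against an artefactual increase in the treatment effect when unplanned interval biopsies remove HSIL tissue and possibly the virus. Protocol 6.4.14 adds that removing tissue early biases results towards improvement in either arm.

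Protocol 1.5 describes usual treatment for cervical HSIL as including "ablative therapy via laser, or cryotherapy" alongside excision, and section 1.2 also names laser ablation. In Protocol 6.12 the list that opens "The following medications and treatments are prohibited" covers glucocorticoids, anti-rheumatic and biologic drugs, vaccines and blood thinners, and no treatment of the lesion. The exclusion criterion on HSIL treatment (Protocol 4.2, no. 4) looks back four weeks from screening only.

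**The concern.** Ablation destroys the lesion and yields no specimen. It can clear HSIL, and possibly HPV-16/18, for reasons unrelated to the assigned treatment, which is the kind of artefact the rule is meant to keep out of the endpoint. The rule does not catch it because it is tied to excision or biopsy. If such a woman meets the Week 36 criteria, her outcome is credited to her randomised arm.

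No planned analysis is certain to score her as a failure. The mITT set applies the same responder definition. The additional per-protocol analysis in SAP 4.3.3 uses the Week 36 result whatever procedure came before it. The primary set is small, so a few such cases would be visible in the estimate. If the rule stays silent, someone will have to decide how to score individual women after the fact.

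**Working it through.** **1. The plan's own figure.** Inputs from SAP 4.1 and Protocol 8.6: 198 randomised 2:1, 33% biomarker-positive, response 66% versus 15%. The test is one-sided at 0.025 (SAP 8.1.1).

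- 198 × 0.33 = 65.3, split 2:1 = 43.6 and 21.8, taken as 44 and 22.
- Miettinen-Nurminen score at zero difference: z = (x1/n1 − x2/n2) / √[p̄(1 − p̄)(1/n1 + 1/n2) · N/(N − 1)], with p̄ = (x1 + x2)/N and N = 66.
- Summing the binomial probabilities of all outcomes with z > 1.96 gives power of 98.8% (99.3% by normal approximation). The stated figure of more than 90% is reproduced and is not in dispute.

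**2. What the rule does with each case between first dose and Week 36.**

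- Excision or biopsy: non-responder (SAP 8.1.1, Table 1).
- Ablation after a post-dose biopsy: already a non-responder because of the biopsy (Protocol 6.4.15).
- Ablation without biopsy or excision, no Week 36 result: non-responder in ITT (SAP Table 1).
- Ablation without biopsy or excision, Week 36 HSIL or HPV-16/18 present: non-responder.
- Ablation without biopsy or excision, Week 36 tissue free of HSIL and HPV-16/18 negative: **meets every responder condition**. All women are scheduled for excision at Week 36 (Protocol 3.5), so a specimen would normally exist.

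Only the last case is a gap.

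**3. Analysis sets for that last case.**

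- ITT: responder.
- mITT (at least one dose, endpoint available): responder.
- PP (all doses, no protocol violation; SAP 4.3.3): undefined, because neither document says whether such treatment is a violation.
- Additional PP analysis: if she is in the PP set, her Week 36 result is used.

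**4. Size of one case.** 1/44 = 2.3 points for VGX-3100; 1/22 = 4.5 points for placebo.

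**5. Effect on the estimate.** Planned rates give 0.66 × 44 = 29 and 0.15 × 22 = 3.3, taken as 3. Miettinen-Nurminen 95% intervals:

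| VGX-3100 | Placebo | Misclassified | Difference (points) | 95% CI |
|---|---|---|---|---|
| 29/44 | 3/22 | none | 52.3 | 28.2 to 68.9 |
| 29/44 | 4/22 | 1 placebo | 47.7 | 22.9 to 65.6 |
| 29/44 | 5/22 | 2 placebo | 43.2 | 17.9 to 62.2 |

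In the other direction, two misclassified VGX-3100 women give 31/44 − 3/22 = 70.5% − 13.6% = 56.8 points.

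**6. Operating characteristics on assumed rates.** The documents give no rate, so the shares below are assumptions. A share a of an arm would otherwise fail but is treated and scored as response, so that arm's rate becomes p + a (44:22, same test).

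- 5% in both arms: power 98.5%.
- Placebo only: power 95.9% at 5% and 89.7% at 10%.
- VGX-3100 only, with both true rates 15%: one-sided rejection rate 3.3%, 6.0% and 13.4% at 2%, 5% and 10%, against 2.1% with none.

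**The case against.** The strongest reply is that the gap is narrow. Suspected progression leads to ad hoc colposcopy and biopsy (Protocol 3.5, 6.4.14, 7.1), and any unscheduled biopsy already makes the woman a non-responder. What remains is a woman treated without a post-dose biopsy or excision, probably outside the study, who still returns for the Week 36 excision and is clear on both components. That stands, and it is why few cases are expected.

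It is also fair that the planned result is robust to misclassification on placebo. With 29/44 held fixed, 8/22 on placebo (five misclassified women) still gives a lower bound of 3.9 points and one-sided p = 0.012. Superiority is lost only at 9/22 (p = 0.027), which needs six of the 19 placebo non-responders to be affected. That direction also works against VGX-3100. The direction that would inflate the effect is possible, but nothing in the documents suggests it is likely.

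Protocol 3.1.4 gives its reason in terms of interval biopsies, so extending that reason to ablation is an inference. It is a short one, since the stated worry is loss of lesion and virus by means other than study treatment.

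Three stronger readings are tempting, and the documents do not support them:

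- *That any such woman is scored as a responder.* She must also have no HSIL and negative HPV-16/18 at Week 36.
- *That this happens in every analysis set.* Absence from the prohibited list does not put her in the PP set. Deviations and PP exclusions are settled with the sponsor before database lock (SAP 5.2), and she may also have missed doses.
- *That HPV-003 shows the error would differ by arm.* The higher LEEP proportion on placebo (Protocol 3.5.1) concerns the Week 36 endpoint procedure. It is not evidence about treatment in the interval, and LEEP is an excision, which the rule covers.

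**Conclusion.** The gap is real: as written, the rule can count lesion-directed treatment before Week 36 as response in the primary ITT and the mITT analyses, and PP handling is undefined. This rests on the wording alone and needs no assumption about frequency.

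The likely effect is small. The per-case shifts assume the planned 33% biomarker-positive share and 2:1 split. The power and rejection rates rest on assumed shares and show sensitivity, not expectation. The stated power is sound. The reason to act is the interpretability of a binary endpoint in about 66 women, and the ease of settling the scoring in advance.

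**What to change.** For the cervical endpoints, extend the failure rule to: *excision, biopsy, or any other treatment directed at the cervical lesion on or after first dose and before the Week 36 tissue sample*. Place it in SAP 4.3.1, 8.1.1 and Tables 1 and 2, and carry it into Protocol 3.1.4, 8.5.1, 8.5.9 and Tables 4 to 9. The non-cervical clearance endpoint keeps its present definition.

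Identify cases by blinded review of the procedures and medications that Protocol 6.12 already has recorded on the CRF. State whether such treatment excludes a woman from the PP set. Settle both before any unblinded result is produced, including the group-level summaries that SAP section 10 allows ahead of database lock.

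This changes scoring only; patient care is unaffected. The cost is one phrase repeated in the listed places and a blinded data check. Response rates may come out slightly less favourable.

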8.1.2. Secondary Efficacy Endpoints

For the secondary efficacy endpoints listed in Section 3.2.2 of this SAP, the analysis method will be the same as for the primary endpoint described in Section 8.1.1, but without p-values.

In addition, the definition of responder and non-responder for each endpoint is defined in Table 2.

Final Statistical Analysis Plan, Version 1.2 Date Issued: 310CT2022

Table 2. Definition of Secondary Endpoints Responder and Non-Responder

Endpoint	Responder	Non-Responder				
Proportion of subjects with no evidence of cervical HSIL on	Subject with no histologic evidence of cervical HSIL ^a at Week 36 ^b	Subject with histologic evidence of cervical HSIL, AIS, cervical carcinoma at Week 36				
histology sample at Week 36 visit	AND	OR				
	Subject in which an excision or biopsy sample ^c was NOT obtained between initial dose up to	Subject in which an excision or biopsy sample was obtained between initial dose up to Week 36				
	Week 36	OR				
		Subjects with no Week 36 sample result				
Proportion of subjects with no evidence of HPV-16 and/or	Subject with no evidence of HPV-16 and/or HPV-18 ^d at Week 36	Subject with evidence of HPV-16 or HPV-18 at Week 36				
HPV-18 in cervical samples by type specific HPV testing at Week 36 visit	AND Subject in which an excision or biopsy sample was	Subject in which an excision or biopsy sample was obtained between initial dose up to Week 36				
	NOT obtained between initial dose up to Week 36	OR				
		Subjects with no Week 36 sample result				
Proportion of subjects with no evidence of squamous atypia,	Subject with no histologic evidence of cervical HSIL, squamous atypia, or LSIL ^e at Week 36	Subject with histologic evidence of cervical HSIL, squamous atypia, LSIL, AIS, cervical carcinoma at Week 36				
LSIL, or HSIL on histology sample at Week 36 visit	AND	OR				
	Subject in which an excision or biopsy sample was NOT obtained between initial dose up to Week 36	Subject in which an excision or biopsy sample was obtained between initial dose up to Week 36				
		OR				
		Subjects with no Week 36 sample result				

Proportion of subjects with no evidence of squamous atypia, LSIL or HSIL on histology sample and no evidence of HPV-16 and/or HPV-18 by type specific HPV testing at Week 36 visit	Subject with no histologic evidence of cervical HSIL squamous atypia, or LSIL at Week 36 and no evidence of HPV-16 and/or HPV-18 at Week 36 AND Subject in which an excision or biopsy sample was NOT obtained between initial dose up to Week 36	Subject with histologic evidence of cervical HSIL, squamous atypia, or LSIL AIS, cervical carcinoma at Week 36 OR Subject with evidence of HPV-16 or HPV-18 at Week 36 OR Subject in which an excision or biopsy sample was obtained between initial dose up to Week 36 OR Subjects with no Week 36 sample result
Proportion of subjects with no progression of cervical HSIL to cervical carcinoma from baseline on histology sample at Week 36 visit	Subject with no histologic evidence of a worsening cervical condition at Week 36 relative to baseline AND Subject in which an excision or biopsy sample was NOT obtained between initial dose up to Week 36	Subject with histologic evidence of worsening of cervical condition at Week 36 relative to baseline OR Subject in which an excision or biopsy sample was obtained between initial dose up to Week 36 OR Subjects with no Week 36 sample result
Proportion of subjects who have cleared HPV-16 and/or HPV-18 on specimens from non-cervical anatomic locations (i.e., oropharynx, vagina and intra-anal) at Week 36 visit	Subject with no evidence of HPV-16 and/or HPV- 18 on specimens from non-cervical anatomic locations ^f at Week 36	Subject with evidence of HPV-16 or HPV-18 on specimens from non-cervical anatomic locations at Week 36 OR Subjects with no Week 36 sample result

Final Statistical Analysis Plan, Version 1.2 Date Issued: 310CT2022

a. No evidence of HSIL is defined by histology as negative, squamous atypia, or LSIL. The first tissue removal sample within the timeframe determines the histology endpoint.

b.The efficacy time frame is defined by those who have undergone a biopsy or surgical excision at any time starting from 14 days prior to the protocol-specified target date of Week 36

c. Excludes ECC-only samples

d. The most recent HPV clearance result prior to first tissue removal, which includes results from the same date, within the time frame determines the HPV clearance endpoint.

e. No evidence of squamous atypia, CIN1, CIN2 or CIN3 on biopsies or excisional treatment

f. Based on HPV-16 and/or HPV-18 positive specimen at baseline. Subjects will be classified according to the presence/absence of HPV-16 and/or HPV-18 at baseline by each of the three anatomic locations.

8.2.Immunogenicity Analyses

Levels of serum anti-HPV-16 and anti-HPV-18 antibody concentrations and Interferon- γ ELISpot response magnitudes will be assessed from sera and PBMCs isolated from whole blood, respectively, collected at baseline, Week 15, and Week 36 visits. Flow Cytometry response magnitudes will be assessed from PBMCs isolated from whole blood collected at baseline and Week 15 visits.

All of the endpoints will be summarized as continuous variables at each visit. Increases from baseline for each post baseline visit from ELISpot and Flow Cytometry, and titers for each post baseline visit from ELISA will be compared between treatment arms. These comparisons will be analyzed with difference in medians and associated exact non-parametric 95% CIs.

The mITT population with at least one immunogenicity measurement will be used for these immunogenicity analyses. Analyses will be performed on the baseline biomarker-positive subjects and on all subjects (regardless of biomarker status) separately.

8.3.Exploratory Analysis

9. Safety Analysis

All safety summaries and analyses will be based on subjects in the safety analysis set. These summaries and analyses will be performed on the baseline biomarker-positive subjects and on all subjects (regardless of biomarker status) separately. Safety listings will flag all subjects who are baseline biomarker positive.

9.1.Adverse Events

A pretreatment event is defined as any event that occurs prior to administration of any study treatment; it does not necessarily have to have a causal relationship with study participation. A treatment emergent adverse event (TEAE) is defined as any event temporally associated with the use of a product whether or not considered related to the use of the product. Adverse event (AE) verbatim reported terms will be coded by SOC and PT using the latest version of MedDRA.

For the purpose of inclusion in AE summaries/analyses, incomplete start and stop dates will be imputed as follows:

Missing start dates will be handled as follows (where UK, UKN and UNKN indicate unknown or missing day, month and year respectively):

- UK-MMM-YYYY: if MMM and YYYY are the same as that of 1st dose, then impute to same date as 1st dose; otherwise impute to 01-MMM-YYYY;
- DD-UNK-YYYY; if DD and YYYY are the same as that of 1st dose, then impute to same date as 1st dose; otherwise impute to DD-JAN-YYYY;
- DD-MMM-UNKN; if DD and MMM are the same as that of 1st dose, then impute to same date as 1st dose; otherwise impute to DD-MMM-YOSCR, where YOSCR is year subject was initially screened;
- UK-UKN-YYYY: if YYYY is the same as that of 1st dose, then impute to same date as 1st dose; otherwise impute to impute to 01-JAN-YYYY;
- UK-MMM-UNKN: if MMM is the same as that of 1st dose, then impute to same date as 1st dose; otherwise impute to 01-MMM-YOSCR, where YOSCR is year subject was initially screened;
- DD-UNK-UNKN: if DD is the same as that of 1st dose, then impute to same date as 1st dose; otherwise impute to impute to DD-JAN-YOSCR, where YOSCR is year subject was initially screened;
- UK-UKN- UNKN: impute to date of subject's 1st dose.

If the imputed start date is after the raw stop date, then the imputed start date will be set as the same as the stop date.

Missing stop dates will be handled as follows (where UK, UKN and UNKN indicate unknown or missing day, month and year respectively):

- UK-MMM-YYYY: impute to the last day of the month;
- DD-UNK-YYYY: impute to DD-DEC-YYYY;
- DD-MMM-UNKN: impute to DD-MMM-YOLV, where YOLV is year of subject's last study visit;
- UK-UKN-YYYY: impute to 31-DEC-YYYY;
- UK-MMM-UNKN: impute to LD-MMM-YOLV, where LD is the last day of MMM and YOLV is year of subject's last study visit;

- DD-UNK-UNKN: impute to DD-DEC-YOLV, where YOLV is year of subject's last study visit;
- UK-UKN- UNKN: impute to day of subject's last study visit.

If the imputed stop date is before the raw or imputed start date, then the imputed stop date will be set as the same as the start date.

AE duration will be calculated as (Stop Date – Start Date) + 1.

AE summary tables will include numbers and percentages of subjects experiencing at least one event by treatment arm. The following is a list of AE summary tables to be generated:

- Overview of AE, AE with onset within 28 days/7 days after study treatment
- TEAEs, TEAEs with onset within 28 days/7 days after study treatment by SOC and PT
- TEAEs, TEAEs with onset within 28 days/7 days after study treatment by Dose Number, SOC and PT
- TEAEs, TEAEs with onset within 28 days/7 days after study treatment by Dose Number, CTCAE Grade, SOC and PT
- Serious TEAEs by Dose Number, SOC and PT
- TEAEs, TEAEs with onset within 28 days/7 days after study treatment by Dose Number, Relationship to IP and EP, SOC and PT
- Serious TEAEs, serious TEAEs with onset within 28 days/7 days after study treatment by Dose Number, Relationship to IP and EP, SOC and PT

• Grade >=3 TEAEs, Grade >=3 TEAEs with onset within 28 days/7 days after study treatment by Dose Number, SOC and PT

• Grade >=3 TEAEs, Grade >=3 TEAEs with onset within 28 days/7 days after study treatment by Dose Number, Relationship to IP and EP, SOC and PT

- TEAEs with Action of Study Treatment Held, TEAEs with Action of Study Treatment Held with onset within 28 days/7 days after study treatment by Dose Number, SOC and PT
- TEAEs with Action of Study Treatment Permanently Discontinued, TEAEs with Action of Study Treatment Permanently Discontinued with onset within 28 days/7 days after study treatment by Dose Number, SOC and PT

Additional AE/SAE summary tables may be added as appropriate.

A subject with 2 or more different adverse events within the same level of the MedDRA term and regimen will be counted only once in that level using the most extreme incident (most severe for the intensity analyses, and related for the relationship to study drug

analyses). For the AE with missing relationship to drug/procedure will be imputed as related. TEAEs by dose will be counted by the AE onset date not earlier than the date of treatment and earlier than the subsequent treatment for the first dose and second dose, and any AEs with onset date on or later than the third dose will all be counted to the third dose.

Data listings will be provided for AE, SAE, TEAE leading to treatment discontinuation, TEAE with CTCAE Grade >=3, TEAE with onset within 28 days/7 days after study treatment, and AEs resulting in death separately.

